Cangrelor is an intravenous adenosine triphosphate (ATP) analogue that directly and reversibly inhibits ADP binding to the adenosine diphosphate (ADP) P2Y₁₂ receptor subtype in a dose-dependent manner, achieving immediate potent platelet inhibition after a bolus dose [1,2]. The cangrelor binding site at the P2Y₁₂ receptor level has been subject to controversy and is not clearly defined [3,4]. Nonetheless, cangrelor is associated with high levels of receptor occupancy and prevents ADP binding. Cangrelor is promptly inactivated through dephosphorylation by ectonucleotidase and has a very short plasma half-life (3-6 minutes) [1-4]. Therefore, recovery of platelet function is rapid (~60 minutes) after discontinuation of cangrelor infusion [1-4].

Cangrelor was approved for clinical use based on the results of the CHAMPION (Cangrelor versus Standard Therapy to Achieve Optimal Management of Platelet Inhibition) PHOENIX trial, which showed that cangrelor significantly reduced the rate of ischemic events, driven by a reduction in stent thrombosis and myocardial infarction, with no significant increase in severe bleeding in patients undergoing percutaneous coronary intervention (PCI) [5]. Given the different pharmacological properties of cangrelor and the oral P2Y₁₂ inhibitors, several studies have investigated the potential for drug-drug interaction (DDI) when these agents are concomitantly administered [6-12]. These potential DDIs are concerning as they can result in reduced platelet inhibition and subsequent lack of protection from thrombotic complications in the peri-PCI period. In a study conducted in healthy volunteers, clopidogrel administration during cangrelor infusion was associated with an impaired antiplatelet effect of clopidogrel after cangrelor discontinuation [6]. This reflects the fact that clopidogrel active metabolite cannot bind to the P2Y₁₂ receptors if already largely occupied by cangrelor. In turn, the plasma concentrations of the unbound clopidogrel active metabolites fall rapidly to subtherapeutic levels

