cangrelor which warrants at least 60 minutes for complete wash-out of effects (thus not adequate to rule out a DDI), and 12.5% of patients had high platelet reactivity at this time point [20]. Moreover, in none of the above mentioned studies were pharmacokinetic (PK) assessments performed to characterize the impact, if any, of cangrelor on systemic levels of ticagrelor and its major metabolite (AR-C124910XX). Therefore, the lack of data to rule out a DDI between cangrelor and ticagrelor when the latter is administered prior to starting cangrelor infusion warrants dedicated prospective investigations. The need for such investigations is underscored by the relatively high prevalence of pretreatment with ticagrelor in acute settings [21,22]. Importantly, such acute settings represent desirable scenarios to use cangrelor. Of note, use of prehospital ticagrelor (i.e, pretreatment) in acute settings is endorsed by practice guidelines both in the United States and Europe [17]. Therefore, ruling out a DDI between cangrelor and ticagrelor when the latter is administered prior to starting cangrelor infusion would have important clinical implications for real-world practice. The methodological approach for this assessment should rely on comprehensive PD assessments aimed to evaluate levels of P2Y₁₂ receptor inhibition and thrombus formation, PK assessments to assess systemic levels of the drug/drug metabolite, and mechanistic assessments by measuring levels of P2Y₁₂ receptor gene expression. In particular, different levels of P2Y₁₂ receptor gene expression can modulate the PD effects of oral P2Y₁₂ receptor inhibitors at a given level of drug exposure defined by PK profiling.

STUDY AIM

The aim of this investigation is to rule out a DDI when ticagrelor is administered prior to cangrelor infusion. Comprehensive PK and PD assessments will be conducted to reach this study aim.

REASERCH PLAN

[figure not shown]
Study design

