will be 2 hours. After completing the first phase of the study, patients will undergo a 1-4 week wash-out period and then will cross-over to the alternative treatment in the second phase (i.e., patients assigned to treatment with cangrelor in the first phase will be assigned to placebo in the second phase and vice-versa). All patients will be on a background of aspirin therapy (81 mg daily maintenance dose). During each phase, PK and PD assessments will be conducted at 7 time points (total 14 time points): baseline (prior to ticagrelor loading dose; time -1 h); at start of cangrelor/placebo bolus and infusion (1 hour after ticagrelor loading dose); 30 minutes after cangrelor/placebo bolus; 1 hour after cangrelor/placebo bolus, 2 hours after cangrelor/placebo bolus (time of infusion discontinuation); 1 hour after discontinuation of cangrelor/placebo infusion; and 2 hours after discontinuation of cangrelor/placebo infusion. Figure 1 illustrates the overall study design. The study will have a double-blind design. Patients, research staff and laboratory personnel will be blinded to treatment assignments. Masking and randomization of medications (cangrelor and placebo) will be performed by our institutional research pharmacy in line with prior investigations [18].

Figure 1. Overall study design

Study Population

Inclusion criteria:

- Patients with known coronary artery disease (defined as prior type I myocardial infarction, coronary revascularization, percutaneous or surgical, or presence of at least a 50% stenosis in any major epicardial vessel).
- Age > 18 years old
- On aspirin 81mg/qd for at least 1 month

Exclusion criteria:

- Inability to provide written informed consent
- Hemodynamic instability
- On treatment with a P2Y₁₂ receptor antagonist (ticlopidine, clopidogrel, prasugrel, ticagrelor) in past 30 days
- Known allergies to ticagrelor or cangrelor
- Considered at high risk for bleeding
- History of intracranial bleeding/hemorrhagic stroke
- On treatment with oral anticoagulant (Vitamin K antagonists, dabigatran, rivaroxaban, apixaban, edoxaban) within past 30 days
- Known platelet count <80x10⁶/mL
- Known hemoglobin <10 g/dL
- Active bleeding
- Known end stage renal disease on hemodialysis
- Known severe hepatic dysfunction
- Acute or severe bronchial asthma or upper airway obstruction.
- Patients with sick sinus syndrome (SSS) or high degree AV block without pacemaker protection.

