In addition to specific assays described above, whole blood, serum and plasma samples will be stored for future analysis that may include genetic determinants of antiplatelet drugs response, alternative mRNAs, and biomarkers.

Study endpoints, sample size calculation and statistical analysis

The primary end point of the study will be the non-inferiority in PRU measured at 2 hours after discontinuation of cangrelor vs. placebo. We hypothesize that in patient receiving

cangrelor following a ticagrelor LD platelet inhibition assessed by PRU will be non-inferior compared to patients receiving ticagrelor LD followed by placebo infusion. Non-inferiority will be assessed using a 95% confidence interval (CI) of the difference in mean PRU between the two arms. Under the assumption of 0 difference in mean PRU between group 1 and group 2 and a common standard deviation of 75 PRU, a sample size of 16 patients will allow for the 95% CI to stay within ± 45 PRU with a 95% power and alpha=0.05. Considering a 25% data attrition rate due to hemolysis, drop out or technical problems, 20 patients will need to be randomized in order to ensure complete available data for analysis. The sample size of this study was established according to results of previous PD investigations [18,30]. In line with previously reported investigations, 45 PRU was chosen for the noninferiority margin for the upper 95% CI limit of the difference [25, 31]. All other end points will be considered exploratory and will include the comparisons of PD and PK parameters, and P2Y₁₂ gene receptor level expression between all treatment arms at each time points, as well as the comparisons of rates of high on-treatment platelet reactivity (HPR). HPR will be defined as PRU>208, PRI>50%, and LTA-ADP>59%, in line with consensus definitions [32].

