Conformity to the normal distribution will be evaluated for continuous variables with the Kolmogorov-Smirnov test. For baseline characteristics, continuous variables will be expressed as mean \pm SD or median [IQR]. Treatment effects will be evaluated comparing the functional parameters observed in the overall patient population after cangrelor treatment with those achieved after placebo regardless of the sequence. All statistical comparisons of platelet function for the primary end point and exploratory end points with continuous variables will be conducted using a linear mixed-effect model with treatment group, sequence, period, and treatment-group-by-period as fixed effects, patient as a random effect, and baseline value of the corresponding

platelet function test as a covariate. The comparisons of rates of HPR will be conducted using the McNemar test.

Platelet reactivity results will be reported as least-square means (LSM) (95% confidence interval [CI]) for the above detailed analyses. LSM differences in PRU between groups and the corresponding 2-sided 95% CI for the difference will be obtained to assess non-inferiority based on the linear model. Given the exploratory nature of comparisons for secondary end points, correction for multiple comparisons will not be performed. A 2-tailed p value of <0.05 will be considered to indicate a statistically significant difference for superiority for all the analyses performed. Statistical analysis will be performed using SPSS version 25.0 software (SPSS Inc., Chicago, Illinois).

The safety population will include all randomized patients exposed to study medication. The PD population will include all patients with PD data and without a major protocol deviation thought to affect significantly the PD and PK of cangrelor or ticagrelor. The PD population will be used for analysis of all primary and secondary end points. Erroneously treated patients (eg, those randomized to one treatment but actually given the other) will be accounted for based on the actual treatment received.

Publication Strategy/Additional Information

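### Does the plan need a non-inferiority rule for PRU at 1 hour after cangrelor, as well as at 2 hours?

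*Combined protocol and SAP*

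**What the plan says.** Under Study design, the last two of the seven samples in each period are taken "1 hour after discontinuation of cangrelor/placebo infusion; and 2 hours after discontinuation of cangrelor/placebo infusion". The endpoints section makes the second of these primary: "The primary end point of the study will be the non-inferiority in PRU measured at 2 hours after discontinuation of cangrelor vs. placebo". Its success rule is also given there: "45 PRU was chosen for the noninferiority margin for the upper 95% CI limit of the difference". Everything else is lower in rank: "All other end points will be considered exploratory and will include the comparisons of PD and PK parameters", and these comparisons are made at each time point, together with rates of high on-treatment platelet reactivity.

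The same section applies one linear mixed model to the primary and to the continuous exploratory end points, and reports least-square means with 95% confidence intervals. It adds "LSM differences in PRU between groups and the corresponding 2-sided 95% CI for the difference will be obtained to assess non-inferiority" without naming a time point, and closes with "A 2-tailed p value of <0.05 will be considered to indicate a statistically significant difference for superiority for all the analyses performed".

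On cangrelor's offset, the Background says "recovery of platelet function is rapid (~60 minutes) after discontinuation of cangrelor infusion". The Study Rationale faults an earlier study for sampling at 30 minutes, when there was still residual effect of "cangrelor which warrants at least 60 minutes for complete wash-out of effects (thus not adequate to rule out a DDI").

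**The concern.** The Study Aim is to rule out a drug-drug interaction and sets no time limit. By the protocol's own wash-out figure, the 1-hour sample is the first that could inform that question and the one closest to cangrelor offset. Yet no sentence attaches the 45 PRU margin, or any other pass rule, to it, and no reason is given for preferring 2 hours to 1 hour. The one decision rule stated for all analyses is a superiority p-value, and a non-significant superiority test does not exclude a loss.

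If ticagrelor's effect were weakened at 1 hour and restored by 2 hours, the primary would pass. A report could then set that pass beside a non-significant 1-hour comparison and claim no interaction throughout. At stake is whether the scope of the headline conclusion is fixed before the data are seen.

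**Working it through.** **The wording**

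1. The Study Rationale gives 60 minutes as a minimum, and the Background gives about 60 minutes as the typical recovery time. The 1-hour sample lies on that limit; the 2-hour sample lies a full hour beyond it.
2. Residual cangrelor lowers PRU in the cangrelor arm, which favours non-inferiority. The later sample is therefore the more demanding place to test that ticagrelor's effect is preserved once cangrelor has gone.
3. The hierarchy is fixed in advance: one confirmatory end point at 2 hours, all others exploratory. A confirmatory statement about 1 hour would contradict the plan.
4. The p<0.05 sentence says what counts as a significant difference for superiority. It gives no meaning to p≥0.05.

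**The size of the risk**

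Inputs from the endpoints section: margin 45 PRU, 16 evaluable patients, 95% power, assumed true difference 0, two-sided 95% interval. The paired SD (SDd) is not given; only a common SD of 75 PRU is. It has to be assumed.

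*SDd implied by the plan's own power.* The normal formula is n = (SDd × (1.960 + 1.645) / 45)². Setting n = 16 gives SDd = 45 × 4 / 3.605 = 49.9. With the noncentral t on 15 df, 95% power needs SDd = 46.6. The plan's power statement therefore implies about 47 to 50. (Taking 75 itself as the paired SD gives n = (75 × 3.605 / 45)² = 36.1, so 37 patients; 16 is not reproduced on that reading.)

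*Chance that a true 45 PRU loss at 1 hour is non-significant.* The standard error is SDd/√16, the noncentrality is 45/SE, and the critical t on 15 df is 2.131. The primary test with true difference 0 and margin 45 has the same noncentrality, so its power is one minus the miss probability.

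| SDd | SE | 45/SE | 1-hour loss of 45 missed | Power of the 2-hour primary |
|---|---|---|---|---|
| 46.6 | 11.65 | 3.86 | 5.0% | 95% |
| 50 | 12.50 | 3.60 | 8.1% | 92% |
| 53 | 13.25 | 3.40 | 11.3% | 89% |
| 75 | 18.75 | 2.40 | 38.8% | 61% |
| 106 | 26.50 | 1.70 | 64.4% | 36% |

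The last two columns sum to 100%. Wherever the 1-hour loss is often missed, the primary is underpowered by the same amount. The 39% and 64% figures therefore measure the sample-size problem, not the lack of a 1-hour rule.

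*Primary passes and the 1-hour loss is missed.* With a true loss of 45 at 1 hour and 0 at 2 hours, simulation gives 7% to 8% of trials at SDd 50, for correlations of 0 to 0.8 between the two differences.

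**Would a 1-hour margin test be clearly better?**

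If the full 45 PRU loss shows in the measurement, such a test passes wrongly in 2.5% of trials. Suppose instead that residual cangrelor masks 20 of the 45 PRU (an illustrative assumption, not in the documents). The measured loss is then 45 − 20 = 25, the distance to the margin is 45 − 25 = 20, and the noncentrality at SDd 50 is 20/12.5 = 1.6. The test passes in 32% of trials (17% at SDd 75, where it is 20/18.75 = 1.07). The added test would thus support a stronger claim at the time point where its error is least controlled, using a margin the plan gives only with the 2-hour end point.

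**The case for a change.** The strongest case for the concern is that the aim is unlimited in time while the test covers one time point, and that the choice of 2 hours is not argued. A fixed-sequence 1-hour test, run only after the primary succeeds, would use planned samples and the planned model and would leave the primary's alpha and power untouched. A superiority p-value cannot stand in for a margin. Losses below 45 PRU would often go undetected: at SDd about 46.6, a true 1-hour loss of 20 or 30 PRU reaches p<0.05 with probability 0.36 or 0.67.

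The facts in this stand. No 1-hour margin exists, 2 hours is not explicitly justified, and absence of significance is not evidence of no loss. They do not amount to a fault. That a transient effect at another time leaves the primary unchanged is true of every single-time-point primary. Losses of 20 or 30 PRU lie inside the margin the plan accepts at 2 hours, and a 45 PRU margin at 1 hour would itself pass a true loss of 20 with probability 0.52. The sequential test is a defensible option with a real drawback, namely residual cangrelor and a borrowed margin, so leaving it out is a design choice. A sentence limiting the confirmatory conclusion to 2 hours would be harmless, but it would only restate what the end-point hierarchy already implies.

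**Conclusion.** The concern does not hold. Followed as written, the plan yields a sound confirmatory conclusion about PRU at 2 hours, past its own 60-minute wash-out, and an exploratory comparison at 1 hour from the same model. The harm needs a reader to take a non-significant superiority test as proof of no interaction, which the plan does not say. Even then, at the paired SD implied by the stated power (about 47 to 50 PRU), a 45 PRU loss at 1 hour is missed in about 5% to 8% of trials with 16 evaluable patients.

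These figures rest on a paired t approximation to the mixed model and on an assumed paired SD. If the true SD is larger, the miss rate rises, but the power of the primary falls by the same amount, and that belongs to the sample-size question. What would be wrong is a report that claimed no interaction from 1 hour on the strength of p≥0.05. That would be an error of reporting, which this plan neither requires nor permits as a confirmatory finding.

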The Switching Antiplatelet Therapy-5 (SWAP-5) study will be a prospective, randomized, double-blind, placebo controlled, cross-over PK and PD investigation aimed to rule out a DDI when ticagrelor is administered prior to cangrelor infusion. Aspirin treated patients with known coronary artery disease will be considered eligible for the study. The study will be performed at the Division of Cardiology of University of Florida Health, Jacksonville, Florida. Patients will be screened by Cardiology Research staff, who will verify that all candidates meet inclusion and exclusion criteria, and obtain their written informed consent to participate in the study. Results from blood tests performed within the last 90 days will be considered valid for screening purposes. If these are not available, a blood sample will be collected for the screening phase.

Using a computer-based randomization system, patients will be randomized in a 1:1 fashion to one of the following treatment arms: a) ticagrelor loading dose followed after 1 hour by cangrelor bolus and infusion or b) ticagrelor loading followed after 1 hour by placebo infusion. In line with FDA recommendations, ticagrelor will be administered as a 180mg loading dose (two 90mg tablets) [23]. Cangrelor will be used at the FDA recommended dose using a 30 μ g/kg bolus followed by 4 μ g/kg/min infusion [19]. The duration of cangrelor/placebo infusion

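### The stated 95% power for 16 patients does not follow from the stated inputs: the 75 PRU SD is not identified, no within-patient correlation is given, and power is 35% to 95% over correlations 0 to 0.81

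*Combined protocol and SAP*

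**What the plan says.** All of this is in the combined protocol and SAP. The section on study endpoints, sample size calculation and statistical analysis sets the planning assumptions: "Under the assumption of 0 difference in mean PRU between group 1 and group 2 and a common standard deviation of 75 PRU". From these it concludes that "a sample size of 16 patients will allow for the 95% CI to stay within ± 45 PRU with a 95% power and alpha=0.05". On the source it says only this: "The sample size of this study was established according to results of previous PD investigations".

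The same section gives the decision rule in two places. The margin is one-sided: "45 PRU was chosen for the noninferiority margin for the upper 95% CI limit of the difference". The interval comes from the mixed model: "LSM differences in PRU between groups and the corresponding 2-sided 95% CI for the difference will be obtained to assess non-inferiority". That model includes a random patient effect and adjusts for the baseline value of the platelet test.

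The Study design section describes a "prospective, randomized, double-blind, placebo controlled, cross-over PK and PD investigation", in which "patients assigned to treatment with cangrelor in the first phase will be assigned to placebo in the second phase and vice-versa". Twenty patients are to be randomized, allowing for 25% attrition. The Publication Strategy section confirms that 20 is the total for the trial, so 16 is a total and not a number per sequence.

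**The concern.** Each patient receives both treatments, so the treatment contrast is a within-patient difference. Its precision depends on the SD of that difference, which equals the per-treatment SD multiplied by √(2(1 − ρ)), where ρ is the within-patient correlation between periods. An SD described as common to two groups reads most naturally as a per-treatment SD. On that reading ρ is essential, and the plan does not give it. If 75 PRU is instead the SD of the difference, no correlation is needed, but the plan does not say so and the power is then far below 95%.

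Non-inferiority in PRU is the only confirmatory test; every other endpoint is exploratory. The number of patients rests on this one power statement. If cangrelor truly has no effect on later ticagrelor inhibition, a 95% power implies a 5% chance of failing to show it. On the printed inputs that chance could be 65%, 39% or 18%, depending on a quantity the plan never states. A failure would then be hard to attribute to an interaction rather than to imprecision.

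**Working it through.** **Inputs from the plan.** True difference 0; SD 75 PRU (type not stated); margin 45 PRU; n = 16 in total; upper limit of the two-sided 95% CI, which is a one-sided test at 0.025.

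**Assumption.** The correlation ρ, shown as a range because the documents give no value.

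**Formulas.** For a 2×2 crossover with n patients:

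- SD of the difference: SDd = 75 × √(2(1 − ρ)) if 75 is the per-treatment SD; SDd = 75 if it is already the paired SD.
- Standard error: SE = SDd / √n = SDd / 4.
- Noncentrality: 45 / SE.
- Power: the probability that a noncentral t with n − 2 = 14 degrees of freedom exceeds the one-sided 0.025 critical value, about 2.145.

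**Attempt to reproduce the 95%.** No reading of the printed inputs with 16 patients in total reaches it:

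| Reading of the inputs (n = 16) | Power |
|---|---|
| 75 as paired SD, one-sided 0.025 | 61% (67% by normal approximation) |
| 75 as paired SD, one-sided 0.05 | 74% (77% by normal approximation) |
| 75 as within-patient SD, or as per-treatment SD with ρ = 0, one-sided 0.025 | 35% (40% by normal approximation) |
| The same, one-sided 0.05 | 49% (52% by normal approximation) |
| 75 as paired SD, both 95% limits within ±45 | about 26% |
| 75 as paired SD, chance that the CI half-width is below 45 | about 77% |

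**Power by correlation**, with 75 as the per-treatment SD, n = 16 and one-sided 0.025:

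| ρ | SDd | SE | 45/SE | Power | Chance of failing when the true difference is 0 |
|---|---|---|---|---|---|
| 0 | 106.1 | 26.5 | 1.70 | 35.2% | 65% |
| 0.5 | 75.0 | 18.75 | 2.40 | 60.8% | 39% |
| 0.7 | 58.1 | 14.5 | 3.10 | 82.1% | 18% |
| 0.75 | 53.0 | 13.3 | 3.39 | 88.4% | 12% |
| 0.80 | 47.4 | 11.9 | 3.79 | 94.1% | 6% |
| 0.81 | 46.2 | 11.6 | 3.89 | 95.1% | 5% |
| 0.90 | 33.5 | 8.4 | 5.37 | 99.9% | 0.1% |

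**What 95% requires.** Solving for SDd at n = 16 gives 46.4 PRU, so ρ = 1 − 46.4² / (2 × 75²) = 0.81. At one-sided 0.05 it gives 52.0 PRU, so ρ = 1 − 52.0² / (2 × 75²) = 0.76.

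**Baseline covariate.** For the covariate alone to bring power to 95%, it would have to remove 1 − 46.4²/75² = 62% of the paired-difference variance if SDd is 75, or 1 − 46.4²/58.1² = 36% if ρ is 0.7.

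**After the plan's own attrition.** 20 × 0.75 = 15 evaluable patients. Power is then 33%, 58%, 79% and 92% at ρ = 0, 0.5, 0.7 and 0.8.

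**The case against.** The strongest reply is that the correlation may well be high. The sample size is said to rest on earlier PD studies, which cannot be consulted here. With ρ near 0.81 the 95% is right, and at 0.90 power is 99.9%. Under the normal approximation 0.78 is enough. The range of 35% to 95% therefore has no special status at either end. It applies only if 75 PRU is the per-treatment SD; if it is the paired SD, power is about 61% whatever the correlation. This stands: what is shown is a figure that cannot be derived from its inputs, not a trial that is certainly too small.

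A second reply is that the missing correlation may be the wrong diagnosis. With 75 as the paired SD and one-sided 0.05, 32 patients (16 per sequence) give 95.3%, so 16 may be a per-sequence number carried over as a total. That is worth checking, but it does not rescue the plan, which fixes the total at 20 and uses a two-sided 95% CI.

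Third, the decision rule can be recovered from the text, so restating alpha and dropping the ± wording is mostly tidying. That is fair. Taken literally, with both limits inside ±45, power would be lower still: about 90% at ρ = 0.81.

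Fourth, the planning SD does not affect the type I error, and the plan will report the estimate with its CI, which helps a reader tell an imprecise result near 0 from a shift upward. This also stands: a positive result would remain valid, and the risk is an inconclusive one. The baseline covariate could raise power too, but the plan gives no size for the gain.

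**Conclusion.** The concern holds. With 16 patients, a true difference of 0 and a 45 PRU margin judged on the upper limit of the two-sided 95% CI, the printed SD of 75 PRU does not deliver 95% power on any reading of it alone. Read as the paired SD, it gives 61%. Read as the per-treatment SD, it gives 35% to 95% over correlations 0 to 0.81, and 95% needs a paired SD of about 46 PRU or less. These figures assume a noncentral t with 14 degrees of freedom and no variance reduction from the baseline covariate. The correlations are assumptions, and the true one may be high enough to support the claim. The power statement for the only confirmatory test should be corrected before anyone relies on it.

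**What to change.** Rewrite the sample-size paragraph:

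1. Say whether 75 PRU is the per-treatment SD or the SD of within-patient differences.
2. State the paired-difference SD, or the correlation, with the earlier PD data set it comes from. While tracing it, check whether 16 was originally a per-sequence number.
3. State alpha as one-sided 0.025.
4. Replace the ±45 PRU wording with the rule actually used: upper limit of the two-sided 95% CI below +45 PRU.
5. Restate the power of 16 evaluable patients on those inputs: about 61% if 75 is the paired SD or the correlation is 0.5, 82% at 0.7, and 95% only at about 0.81 (paired SD about 46 PRU).
6. If a gain from the baseline covariate is assumed, give its size.

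The cost is one paragraph of wording and one look-up in the sponsor's earlier PD data, with no added patients or procedures. The 95% stays if those data, with any stated covariate gain, support a paired SD of about 46 PRU or less. Otherwise the stated power falls.

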**Pharmacodynamic and pharmacokinetic profiles of switching between cangrelor and
ticagrelor following ticagrelor pre-treatment:
The Switching Antiplatelet -5 (SWAP-5) study**

[name]
Assistant Professor of Medicine
Division of Cardiology
University of Florida College of Medicine - Jacksonville
[name]
[name]
[contact], [contact]
[contact]

PROJECT SUMMARY

Cangrelor is an intravenous P2Y₁₂ inhibitor utilized as a bridge to achieve adequate platelet inhibition until oral P2Y₁₂ inhibitors achieve their full antiplatelet effects in patients undergoing coronary stenting. Although in this setting the potent oral P2Y₁₂ inhibitor ticagrelor is commonly utilized, there is very limited data on the optimal approach for switching between these therapies. In particular, ruling out a drug-drug interaction (DDI) is critical to this extent as the presence of a DDI would translate into reduced or abolished antiplatelet effects exposing these acute patients to an increased thrombotic risk. Despite the available evidence suggesting a lack of DDI with the use of ticagrelor in cangrelor treated patients, most data derive from studies in which ticagrelor was given at the time of initiation or during cangrelor infusion. To date, there is no data to fully rule out a DDI when ticagrelor is given prior to starting cangrelor infusion. The need for such investigation is underscored by the relatively high prevalence of pretreatment with ticagrelor in acute settings. The methodological approach for this assessment should rely on comprehensive pharmacodynamics (PD) investigations aimed to assess levels of P2Y₁₂ receptor inhibition, pharmacokinetic (PK) investigations to assess systemic levels of the drug/drug metabolite, and mechanistic investigations by assessment of levels of P2Y₁₂ receptor gene expression. The overarching aim of this investigation is to rule out a DDI when ticagrelor is administered prior to cangrelor infusion.

BACKGROUND

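### The 95% power is stated for a two-sided ±45 PRU condition, not for the upper-limit non-inferiority rule, and 16 patients with an SD of 75 PRU give 95% under neither

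*Combined protocol and SAP*

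**What the plan says.** All the relevant text is in the combined protocol and SAP, mostly under *Study endpoints, sample size calculation and statistical analysis*.

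- **Endpoint:** "The primary end point of the study will be the non-inferiority in PRU measured at 2 hours after discontinuation of cangrelor vs. placebo".
- **Method:** "Non-inferiority will be assessed using a 95% confidence interval (CI) of the difference in mean PRU between the two arms". This sentence names no limit.
- **Sizing assumptions:** "Under the assumption of 0 difference in mean PRU between group 1 and group 2 and a common standard deviation of 75 PRU". The text does not say whether 75 PRU is the SD of one measurement or of the within-patient difference, and it gives no correlation.
- **Sizing claim:** "a sample size of 16 patients will allow for the 95% CI to stay within ± 45 PRU with a 95% power and alpha=0.05". The sidedness of alpha is not given.
- **Margin:** "45 PRU was chosen for the noninferiority margin for the upper 95% CI limit of the difference".
- **Analysis:** later in the same section, "the corresponding 2-sided 95% CI for the difference will be obtained to assess non-inferiority based on the linear model".

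The Project Summary describes the feared interaction in one direction only: "the presence of a DDI would translate into reduced or abolished antiplatelet effects". The plan defines high on-treatment reactivity as PRU above 208, so a higher PRU means less inhibition. Harm is therefore a positive cangrelor-minus-placebo difference, although the plan does not write down the direction of subtraction.

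**The concern.** Keeping the whole interval inside ±45 PRU is a two-sided condition of the equivalence type. Keeping the upper limit below 45 PRU is a one-sided non-inferiority condition. The only power statement in the plan is attached to the first, and the test is the second.

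The power figure is the plan's main argument that 16 evaluable patients are enough. If the trial misses its margin, readers will interpret that result against a claimed 95% chance of success. They need to know which rule the figure describes and which SD produces it. The ± wording, next to a stated aim of excluding an interaction, could also lead a reader to expect a two-directional conclusion that the test does not provide.

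**Working it through.** **Inputs from the plan:** n = 16, margin m = 45 PRU, true difference 0, SD 75 PRU, two-sided 95% CI (one-sided 0.025 for the upper limit).

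**Assumptions:** s, the SD of the within-patient difference, is not stated and is varied. For the t calculations I use 14 degrees of freedom (16 patients, two sequences).

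**Formulas:** SE = s/√16 = s/4.
- Upper-limit rule: power = Φ(m/SE − 1.960). The t version is the upper tail of a noncentral t with noncentrality m/SE, beyond t(0.975; 14) = 2.145.
- ±45 rule: power = 2Φ(m/SE − 1.960) − 1. The t version averages over the sampling distribution of the estimated SD.

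**Attempt to reproduce the 95%, taking s = 75.** SE = 18.75 and m/SE = 2.40.
- Upper limit: Φ(0.44) = 67%; t version 61%.
- ±45: 2 × 0.670 − 1 = 34%; t version 26%.
- With one-sided 0.05 instead, the upper-limit rule reaches 77% (t: 74%) and the ±45 rule 55% (t: 48%).

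**Taking 75 as the SD of one measurement with zero correlation.** s = 75√2 = 106.1 and SE = 26.5. The upper-limit rule has 40% (t: 35%) and the ±45 rule about 0% (t: 2%).

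**Taking the sentence as a precision statement.** With s = 75 the expected half-width is 1.96 × 18.75 = 36.8 PRU, or 40.2 PRU with t. Both are below 45. But the half-width falls below 45 with a probability of only about 77 to 79% (14 or 15 degrees of freedom), not 95%.

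None of these readings gives 95%.

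**What would give 95% with n = 16.**
- Upper-limit rule: 45/SE = 1.960 + 1.645 = 3.605, so s = 180/3.605 = 49.9 PRU. The t version gives 46.4.
- ±45 rule: 45/SE = 2 × 1.960 = 3.920, so s = 180/3.920 = 45.9 PRU (normal approximation).
- If 75 is the per-measurement SD, s² = 2 × 75² × (1 − ρ), so ρ = 1 − s²/11,250. This gives 0.78 for s = 49.9 and 0.81 for s = 45.9 or 46.4. The value s = 75 corresponds to ρ = 0.50.

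**How far the two conditions part, at a true difference of 0 (t version).**

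| s (PRU) | Upper limit < 45 | CI within ±45 | Passes first, fails second |
|---|---|---|---|
| 46 | 95% | 91% | 5% |
| 50 | 92% | 83% | 8% |
| 60 | 80% | 60% | 20% |
| 75 | 61% | 26% | 35% |

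The disagreement runs one way: any interval inside ±45 also has its upper limit below 45. At the plan's assumed zero difference, disagreement above about 5 to 8% appears only at SDs where the upper-limit rule is itself short of 95% power. Those rows mainly show lack of power, not the effect of the wording. If cangrelor truly left PRU lower, the disagreement would be larger (20% at −10 PRU with s = 50, normal approximation), but the margin sentence still decides that case.

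**The case against.** The strongest reply is that the plan has one decision rule. The endpoint, the hypothesis, the margin sentence and the analysis paragraph all speak of non-inferiority, and the margin is tied to the upper limit. The ± wording occurs once, as a description of what 16 patients should deliver. Nowhere is a lower limit above −45 made a condition of success. That stands. A reader might infer two competing pass criteria, with the choice left open until the data are seen; the text does not support this. If the lower limit fell below −45 and the upper limit stayed below 45, the margin sentence would say that non-inferiority is met.

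A second reply is that sizing for ±45 is conservative, since its power is a lower bound on power for the upper-limit rule. That is correct at any given SD, and the wording does not inflate the non-inferiority error rate. It does not rescue the 95%, which neither rule yields from the stated inputs.

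Third, 75 PRU may be a per-measurement SD with high within-patient correlation, and baseline adjustment may reduce the residual SD further. Both are possible, and 95% could then be right. But the plan would be relying on a correlation near 0.8 that it does not state.

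A reader might also infer that excluding an interaction requires limits in both directions. The Project Summary defines the concern as a reduced or abolished effect, which the upper-limit rule addresses.

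**Conclusion.** The point holds as a mismatch between the power statement and the decision rule, combined with a power figure that cannot be reproduced. With 75 PRU as the SD of the within-patient difference and a true difference of 0, power is about 61% (67% normal) for the rule that decides the trial and 26% (34% normal) for the condition named in the sizing sentence. For the upper-limit rule, 95% requires an SD of the difference of about 46 to 50 PRU.

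These results rest on 16 evaluable patients, a one-sided level of 0.025, and an assumed SD of the difference. They do not show that the trial is underpowered, because the plan does not say which SD 75 PRU is. They show that its stated inputs do not support the stated 95%. The intended rule can be inferred, so this is a correction to make before analysis and not a flaw in the test itself.

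**What to change.** 1. **State the rule in full.** Remove the ±45 wording and write that non-inferiority is met if the upper limit of the two-sided 95% CI for the least-squares mean PRU difference, cangrelor minus placebo, at 2 hours after the infusion is stopped, is below +45 PRU (one-sided 0.025).
2. **Complete the sizing inputs.** Say whether 75 PRU is a per-measurement SD or the SD of the within-patient difference. Give the SD of the difference, or the correlation, with its source.
3. **Restate the power** that 16 evaluable patients give for that rule: about 95% if the SD of the difference is 46 PRU, 92% at 50, 80% at 60 and 61% at 75.
4. **Match the conclusion to the rule:** no loss of platelet inhibition greater than 45 PRU, with the lower limit reported descriptively.

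The cost is a few sentences of wording and one figure from the sponsor's earlier data. No patients, assays or design changes are asked for. The downside is that the restated power may be less favourable than 95%: with an SD of the difference of 75 PRU, 95% power for the upper-limit rule would need (75 × 3.605/45)² = 36.1, that is 37 patients. The plan would then have to state the lower power openly.
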